## STATISTICAL ANALYSIS PLAN

**Figure 10.1 Cumulative recurrent infection free probability until day 63 from PCR uncorrected and days by treatment in Burkina Faso**

**Figure 10.2 Cumulative recurrent infection free probability until day 63 from PCR uncorrected and days by treatment in DRC Congo**

**Figure 10.3 Cumulative recurrent infection free probability until day 63 from PCR uncorrected by treatment in Gambia**

**Figure 10.4 Cumulative recurrent infection free probability until day 63 from PCR uncorrected by treatment in Guinea**

**Figure 10.5 Cumulative recurrent infection free probability until day 63 from PCR uncorrected by treatment in Niger**

**Figure 10.6 Cumulative recurrent infection free probability until day 63 from PCR uncorrected by treatment in Nigeria**

**Figure 10.7 Cumulative recurrent infection free probability until day 63 from PCR uncorrected by treatment in Tanzania**

**Figure 10.8 Cumulative recurrent infection free probability until day 63 from PCR uncorrected and days by treatment in Rwanda**

**Figure 10.9 Cumulative recurrent infection free probability until day 63 from PCR uncorrected and days by treatment in all sites**

### **3.4 Safety and tolerability of ACTs and TACTs within and across sites and regions, including comparisons of 'non-matching' ACTs vs TACTs (AL+Placebo versus ASMQ+PPQ, ASMQ+Placebo versus AL+AQ).**

Safety analyses will be based on the whole population that get administered the study drug. That is, the safety and tolerability data will be pooled from all the sites that received the same antimalarial treatment. Safety and tolerability of TACTs versus ACTs will be assessed by comparing the frequency (%) of adverse events and serious adverse events, with particular attention to abdominal pain, appetite perturbation, biochemical markers of hepatic and renal toxicity and QT interval prolongation, using the Fisher's exact test. Safety data will be presented in tabular and/or graphical format and summarized descriptively. Any clinically relevant abnormalities or values of potential clinically concern will be described. Patients will be analysed following the intention to treat analysis. All adverse event summaries will refer to treatment emergent adverse events, i.e. adverse events that newly started or increased in intensity after the study drug administration. Adverse events will be graded according to Division of AIDS table for grading the severity of ADULT AND PEDIATRIC adverse Events Version 2.0, November, 2014. The relevant DAIDS table will be appended to this document. The safety and tolerability summaries will be presented in tables 6.

The frequency and proportion of subjects that reports completing a full course of observed TACT or ACT without withdrawal of consent or exclusion from study because of drug related serious adverse events will be summarized within and across sites and regions. The 95% confidence intervals will be reported for the proportions. The proportions will be compared between matching drugs. The analyses will be summarised in table 7.

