4.2. Secondary objectives

- To compare the safety and tolerability of ACTs and TACTs within and across sites and regions, including comparisons of 'non-matching' ACTs vs TACTs (AL+PBO versus ASMQ+PPQ, ASMQ+PBO versus AL+AQ).
- To compare additional measures of treatment efficacy between treatment arms, including the 63-day ACPR, the post-treatment prophylactic effect of ACTs and TACTs defined as the 42-day and 63-day PCR uncorrected ACPR, gametocyte carriage, parasite clearance rates and fever clearance.
- To assess pharmacokinetic and pharmacodynamic interactions between antimalarials in TACTs

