7. PROPOSED ACTIVITIES

Subjects will be randomized to up to four arms: artemether-lumefantrine + amodiaquine, artemether-lumefantrine + placebo, artesunate-mefloquine + piperazine and artesunate-mefloquine + placebo. As a contingency measure in case of significant differences in the efficacy or safety of one of the combinations being tested and/or study drug expiry or unavailability, subjects may be randomized to 2 arms with a matching ACT-TACT pair, i.e., with artemether-lumefantrine + placebo or artemether-lumefantrine + amodiaquine OR artesunate-mefloquine + placebo or artesunate-mefloquine + piperazine.

Some sites may randomize between 2 arms only with matching ACT-TACT pairs, i.e., artemether-lumefantrine + placebo or artemether-lumefantrine + amodiaquine OR artesunate-mefloquine + placebo or artesunate-mefloquine + piperazine. In Rwanda, subjects will be randomized between 2 arms consisting of artemether-lumefantrine + placebo or artemether-lumefantrine + amodiaquine.

In the control arms, the ACT will be co-packed with a matched (appearance) placebo.

In lower transmission settings (Annual Parasite Incidence <50 per 1000 population per year) the treatment will include a single 0.25 mg/kg gametocytocidal dose of primaquine as recommended by the WHO for children ≥ 10 kg. All drug administrations will be observed.

Subjects will be treated in an in-patient unit for 3 days and followed up weekly up to D63. Microscopy to detect and quantify malaria parasitaemia will be performed daily (more frequently in patients with parasite density of $>5000/\mu\text{L}$ at inclusion) during hospitalization, at all weekly and unscheduled visits. A physical examination and measurements of vital signs along with a symptom questionnaire for tolerability will be performed and recorded through a standardized method at baseline, daily during admission and weekly during follow up through D42 and at all unscheduled visits. Physical exam, vital sign measurements and assessments of symptoms will be performed on D49, D56, and D63 only for patients who are parasitaemic or those who report fever or other symptoms. Electrocardiographs will be performed during admission (H0, H4, H52 or H64) and day 42 of follow up to assess and compare the effect of ACTs and TACTs antimalarials on QT or QTc intervals.

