8.2. Inclusion criteria

- Male or female, aged ≥ 6 months to < 12 years (For Gambia, Rwanda sites only: ≥ 6 months)
- Ability to take oral medication
- Acute uncomplicated *P. falciparum* mono-infection
- Asexual *P. falciparum* parasitaemia: 1,000/ μ L to $\leq 10\%$ parasitaemia, determined on a peripheral blood film (For Gambia, Rwanda sites only: For subjects ≥ 12 years – 1000/ μ L to 200,000/ μ L)
- Fever defined as $> 37.5^{\circ}\text{C}$ tympanic temperature or a history of fever within the last 24 hours
- Written informed consent by the subject or by parent/guardian in case of children lower than the age of consent and assent if required (per local regulations)
- Willingness and ability of the subjects or parents/guardians to comply with the study protocol for the duration of the study

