## STATISTICAL ANALYSIS PLAN

H52	XXX.X (XX.X)	XX.X (XX.X)	0.XXX									
H60	XXX.X (XX.X)	XXX.X (XX.X)	0.XXX									
H64	XXX.X (XX.X)	XXX.X (XX.X)	0.XXX									

**3.6 Assessing and comparing *P. falciparum* parasite clearance rate, additional parameters of parasite clearance dynamics and fever clearance time of standard ACTs and matching TACTs.**

Parasite clearance half-life, proportion of subjects with microscopically detectable *P. falciparum* parasitaemia at Day 3 and fever clearance time (i.e. the time taken for the tympanic temperature to fall below 37.5 °C in patients who were febrile at inclusion) will be summarized and presented in table 9 below. In addition, proportion of subjects with gametocytaemia during and after treatment stratified by presence of gametocytes at enrolment will be presented in tables 9 and 10 below.

**Table 9. Parasite clearance half-life, microscopy *P. falciparum* positivity and fever clearance time (up to H72 vs after H72)**

Arms	Median Time (hours) to Resolution of Fever (range) *	Median Parasite Clearance Half-Life in hours (range) **	Median Time (hours) to 50% Parasite Clearance (range) **	Median Time (hours) to 90% Parasite Clearance (range) **	Parasite Clearance Half-Life >5 hours, (n/N) % (95% CI) **	Positive for Parasitaemia on day 3, (n/N) % (95% CI) ***
AL based overall	XX.X (XX.X-XX.X)	XX.X (XX.X-XX.X)	XX.X (XX.X-XX.X)	XX.X (XX.X-XX.X)	(XX/XX) X(X-X)	(XX/XX) X(X-X)
AL+AQ	XX.X (XX.X-XX.X)	XX.X (XX.X-XX.X)	XX.X (XX.X-XX.X)	XX.X (XX.X-XX.X)	(XX/XX) X(X-X)	(XX/XX) X(X-X)
AL+Placebo	XX.X (XX.X-XX.X)	XX.X (XX.X-XX.X)	XX.X (XX.X-XX.X)	XX.X (XX.X-XX.X)	(XX/XX) X(X-X)	(XX/XX) X(X-X)
ASMQ based overall	XX.X (XX.X-XX.X)	XX.X (XX.X-XX.X)	XX.X (XX.X-XX.X)	XX.X (XX.X-XX.X)	(XX/XX) X(X-X)	(XX/XX) X(X-X)
ASMQ +PPQ	XX.X (XX.X-XX.X)	XX.X (XX.X-XX.X)	XX.X (XX.X-XX.X)	XX.X (XX.X-XX.X)	(XX/XX) X(X-X)	(XX/XX) X(X-X)

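### Pooled non-matching safety comparisons (AL-based versus ASMQ-based) are partly between countries, because Rwanda contributes only to the AL arms and no stratification by site is planned

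*SAP*

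**What the plan says.** **Objective.** Protocol 4.2 sets a secondary objective "To compare the safety and tolerability of ACTs and TACTs within and across sites and regions". It expressly extends this to two pairs that cross the drug families: AL+PBO with ASMQ+PPQ, and ASMQ+PBO with AL+AQ. SAP 2.1.3 and the heading of SAP 3.4 repeat it.

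**Method.** SAP 3.4 defines the population thus: "Safety analyses will be based on the whole population that get administered the study drug". It explains this by adding that "the safety and tolerability data will be pooled from all the sites that received the same antimalarial treatment". Adverse event frequencies are then compared "using the Fisher's exact test". Neither document stratifies these comparisons by site, adjusts them for site, or limits them to sites that randomised both arms.

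**Arms by site.** The protocol synopsis and sections 7 and 10.1 give Rwanda two arms, AL+PBO and AL+AQ. The other seven sites are planned with four. Protocol 7 also says "Some sites may randomize between 2 arms only with matching ACT-TACT pairs", and allows a fall-back to one matching pair for reasons that include drug supply.

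**Age.** Protocol 8.2 limits entry to children under 12, with the exception "For Gambia, Rwanda sites only: ≥ 6 months".

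**Related display.** Table 9 in SAP 3.6 has summary rows by drug family, one labelled "AL based overall" and a counterpart for ASMQ.

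**The concern.** Randomisation protects a comparison only among subjects who could have been allocated to either arm. No Rwandan subject can be allocated to ASMQ. If the arms are built by treatment over all sites and compared in a single two-by-two table, Rwandan subjects enter the AL side with nothing to balance them on the ASMQ side.

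Rwanda also differs by design. It enrols adolescents and adults, and those aged 12 or over have their own parasitaemia and haematocrit limits (Protocol 8.2, 8.3). Table 6 lists symptoms such as headache, nausea, dizziness and blurred vision, whose reporting may plausibly vary with age and site. A difference in event rates between Rwanda and the other countries could then be read as a difference between AL-based and ASMQ-based treatment.

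**Working it through.** **Inputs.** 216 subjects in Rwanda and 432 at each of seven other sites (synopsis); 72 per ACT arm and 144 per TACT arm at each site (Protocol 15.1); ACT to matching TACT allocation 1:2 (SAP 2.2). The Rwandan split of 72 and 144 is inferred from 216 and that ratio.

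**1. Planned total.** 7 × 432 + 216 = 3,240, as the synopsis states.

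**2. Pooled arms in Africa.**
- AL+PBO: 8 × 72 = 576
- AL+AQ: 8 × 144 = 1,152
- ASMQ+PBO: 7 × 72 = 504
- ASMQ+PPQ: 7 × 144 = 1,008

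These sum to 3,240. Rwanda's share is 72/576 = 144/1,152 = 12.5% of each AL arm and 0% of each ASMQ arm.

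**3. Age mix.** Rwanda and The Gambia have no upper age limit. Together they supply 2 × 72/576 = 25.0% of each AL arm. The Gambia alone supplies 72/504 = 14.3% of each ASMQ arm. The Gambia has all four arms, so the imbalance comes from Rwanda.

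**4. Bias with no drug effect.** Let r be the event rate elsewhere and r_R the rate in Rwanda. The pooled AL rate is 0.875r + 0.125r_R and the ASMQ rate is r. The spurious difference is 0.125 × (r_R − r).

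**5. False-positive rate.** The documents give no event rates by site, so the pairs below are assumptions. On the AL side the count is binomial(504, r) plus binomial(72, r_R), or binomial(1,008, r) plus binomial(144, r_R). On the ASMQ side it is binomial(1,008, r) or binomial(504, r). The probability that two-sided Fisher gives p ≤ 0.05 was summed over all outcomes of non-negligible probability.

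| Elsewhere / Rwanda | Bias, points | AL+PBO vs ASMQ+PPQ (576 vs 1,008) | AL+AQ vs ASMQ+PBO (1,152 vs 504) |
|---|---|---|---|
| 1% / 1% | 0 | 4% | 3% |
| 1% / 3% | 0.25 | 6% | 4% |
| 10% / 15% | 0.625 | 6% | 6% |
| 10% / 20% | 1.25 | 12% | 10% |
| 5% / 15% | 1.25 | 17% | 15% |
| 10% / 30% | 2.5 | 32% | 29% |

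To imitate the whole 1% to 3% difference used in Protocol 15.1, Rwanda's rate would have to be 0.01 + 0.02/0.125 = 17%.

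**6. Power with and without Rwanda, 1% versus 3%, two-sided 5%.** Protocol 15.1 claims power above 80% for the matching comparisons. An unpooled normal test reproduces this: 86.6% (576 vs 1,152) and 81.9% (504 vs 1,008). Fisher, the planned test, gives less: 77.8% and 70.6%. For the non-matching contrasts Fisher gives 75.6% (576 vs 1,008) and 72.0% (504 vs 1,152) with Rwanda pooled in, and 70.6% (504 vs 1,008) without it. The losses are 5.0 and 1.4 points.

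**The case against.** **No table shell shows a non-matching test.** Table 6 has no p-values, Table 7a tests matching pairs only, and the text on treatment completion speaks of matching drugs. This stands, and it lowers the weight of the point. It does not remove it: the objective and the section heading promise the comparison, and the only method given is pooled and unstratified.

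**The pooling sentence might be meant to leave Rwanda out of contrasts with ASMQ.** It does not say so, and the whole-population sentence before it points the other way.

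**The objective includes comparison within sites.** In a four-arm site these contrasts are fully randomised and would help to expose an artefact from Rwanda. That is a partial safeguard, but the SAP gives no method for making or combining site-level comparisons.

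**The larger error rates need twofold or threefold rate differences.** This is right. At 1%/3% and 10%/15% the error is close to nominal.

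**Protocol 15.1 also plans a pool with DeTACT-Asia.** Rwanda would then be 72/918 = 7.8% of AL and 144/1,494 = 9.6% of AL+AQ, so the dilution is greater there.

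**Stronger readings that a reader might infer.** One is that the non-matching contrasts are not randomised at all. The plan does not support it: 87.5% of each AL arm comes from sites planned with all four arms. Another is that resistant Rwandan infections distort Table 9. That table carries no tests and sits under a heading about matching comparisons. Protocol 3.2 reports only early signs of resistance in the country, so resistance in enrolled subjects is presumed. Protocol 7 plans clearance rates in about 250 patients without stating Rwanda's share, so 12.5% cannot be carried over.

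**Conclusion.** The point holds as a limited one. The rule in SAP 3.4 makes the pooled non-matching safety contrasts partly between-country, through the one-eighth of each AL arm that comes from Rwanda. The bias is 0.125 times the rate gap. It is negligible for rare events and material only for common symptoms that differ strongly between Rwanda and the other sites.

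This rests on the planned arm sizes, the inferred 72/144 split in Rwanda, and assumed site rates. If other sites use the two-arm option in Protocol 7, the imbalance could grow.

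Severity is low. Only secondary safety contrasts are touched. The primary endpoint is compared between matching arms within each site, and pooled matching comparisons within Africa are not affected by Rwanda, which contributes to both AL arms in the same 1:2 ratio as the other sites.

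**What to change.** Add to SAP 3.4 that the non-matching safety contrasts are stratified by site (for example Mantel-Haenszel or an exact stratified test). They should use only sites in which both compared arms were open to randomisation, and only such periods within a site if the two-arm contingency in Protocol 7 is used. Rwanda then contributes only to the matching AL comparison, and its safety data can be shown separately.

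In Table 9, a footnote is enough: the AL summary row includes Rwanda and the ASMQ summary row does not.

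The cost is a sentence or two of SAP text. Each non-matching contrast becomes 504 versus 1,008, and Fisher power for 1% versus 3% falls from 75.6% to 70.6% and from 72.0% to 70.6%. These figures use a single-table Fisher test. Power under the stratified test will depend on the version chosen, because at a 1% rate an ACT arm expects only 72 × 0.01 = 0.72 events per site, so the SAP should name the version. The matching comparisons lose nothing.

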Whether this 'mutual exclusiveness' represents a role of *pfmdr1* in piperazine resistance (for instance by restricting the amount of piperazine entering the food vacuole) or is simply the effect of a relative low mefloquine pressure in the last decade in Cambodia and Vietnam needs further investigation. Importantly, although in low frequency, parasites bearing both markers of mefloquine resistance and piperazine resistance (*pfmdr1* and *pfplasmepsin2-3* amplification, respectively) have been found in field isolates [16], and its prevalence was recently reported to have increased in Preah Vihear province in Cambodia, after the reintroduction of artesunate-mefloquine as first line treatment [17]. The consequence of the double amplification of *pfmdr1* and *pfplasmepsin2-3* for efficacy of the TACT DHA-piperazine-mefloquine has not been established.

An increase in the QTc-interval following intake of the antimalarials piperazine and amodiaquine has been described [18-22]. In the recent TRACII study conducted primarily in adults, we also observed that the QTc interval increased after administration of DHA-piperazine by a mean of around 20 milliseconds. Reassuringly, the addition of mefloquine to DHA-piperazine did not lead to a further increase of the QTc-interval. Further, the incidence of a QTc prolongation following treatment of more than 60 milliseconds was comparable between subjects treated with DHA-piperazine and DHA-piperazine + mefloquine. Data from the TRACII study also confirmed that a treatment with artemether-lumefantrine does not prolong the QTc-interval whereas the addition

of amodiaquine to artemether-lumefantrine prolonged the QTc-interval by about 10 milliseconds over the first 64 hours, which conforms to what has been previously described for amodiaquine. Amodiaquine did not increase the incidence of a QTc-prolongation >60 milliseconds above baseline, which is rare in the treatment with artemether-lumefantrine alone (about 1 in 300 treatments). Any antimalarial treatment is associated with a drop in the heart rate in the first day of treatment. As the fever and/or clinical illness subsides the heart rate generally decreases. The TRACII study confirmed previous findings that amodiaquine use is associated with a bigger decrease in heart rate compared to other antimalarials and a higher incidence of bradycardia (<54 beats/minute), both in adults and children.

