Therefore, we aim to conduct a large scale randomized clinical trial in up to 8 African countries to compare the efficacy, safety and tolerability of the TACTs artemether-lumefantrine+amodiaquine and artesunate-mefloquine+piperaquine and the standard ACTs artemether-lumefantrine+placebo, and artesunate-mefloquine+placebo. Early signs of independent emergence of artemisinin resistance have recently been detected in Rwanda [24]. This implies that there may soon be an urgent need to deploy novel treatments such as the TACTs

being tested in this trial if the ACTs being used as first-line treatments start to fail in the country. High coverage of malaria control interventions across Rwanda which have led a steep reduction in the incidence of malaria across the country, including in the north-west where the artemisinin resistance was detected and also where this study will be conducted. Accordingly, to ensure that the target sample size is reached, this study will be conducted in Rwanda with only 2 arms. The TACT artemether-lumefantrine-amodiaquine will be compared with artemether-lumefantrine with respect to efficacy, safety and tolerability given that this TACT could be more readily deployed if needed to replace ACTs.

Given that the observations of low incidence of QTc prolongation are from a relatively small population, they need further monitoring and confirmation. Accordingly, in this study electrocardiograph measurements (ECGs) will also be performed at baseline and several time points thereafter to assess the effect of antimalarials on the QT/QTc interval.

In addition to the main clinical outcomes of the study, we aim to assess the extent of the spread or the de novo emergence of resistance to the antimalarials in the combinations through detailed in vivo and in vitro assessments and to study the pharmacokinetics and inter-drug interactions of the drugs, the parasite- and host-related factors affecting treatment outcomes. Finally, we aim to gain insights into the spread of resistance mediated by population movements and parasite gene flows in general through travel surveys and geographic localization of parasite genetic data.

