15. STATISTICAL CONSIDERATIONS

15.1. Sample size justification

These studies will have a non-inferiority trial design. Each site will be powered for the efficacy endpoint. For the safety and tolerability endpoint, the sample size will be pooled across the study

sites to achieve the desired power of at least 80% to detect rare events.

For sample size calculations, the following assumptions have been used: The expected efficacy of ACTs (AL, ASMQ) in these countries is expected to be approximately 96%. The matching TACT efficacy is assumed to be at least 90% under the null hypothesis of inferiority based on the WHO 90% efficacy threshold. However preliminary TRACII study data suggest that TACTs potentially may have a better efficacy of 1% to 2% higher in favour of TACT (i.e. a conservative 97%-98% efficacy or higher).

A one-sided alpha of 0.025 has been used in sample size calculations as non-inferiority is in one direction. For the efficacy outcome, a sample size of 60 subjects in the ACT plus placebo arms and 120 subjects in the matching TACT would be needed to achieve approximately 80% power to detect a non-inferiority margin difference between the group efficacy of -6%. With an additional 20% to cover for loss to follow up, we would therefore need 72 subjects in ACT plus placebo group and 144 subjects in the matching TACT in each of the sites. Since there will be 4 arms, it means we will need 432 subjects per site with 144 subjects in the two ACT arms combined and 288 subjects in the two TACT arms combined.

The sample sizes are in the ratio of 1:2 for ACT vs TACT to allow us to collect more safety and tolerability data for TACTs, which could be beneficial to both policy makers as well as future malaria patients [26, 27]. With these numbers of recruited subjects in Africa, we will have a power above 80% to detect an increase of the incidence of adverse events from 1 in 100 to 3 in 100 for subjects treated with ACT as compared to the matching TACT, respectively.

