19.4.3. Risks of artesunate-mefloquine

Side effects such as nausea and vomiting, dizziness and headache have shown to be consistently associated with ASMQ. Other adverse effects following treatments with ASMQ are fatigue, nightmares and anxiety. Palpitations are also relatively more common with AS+MQ. Mild prolongations of QTc intervals have been reported following ASMQ treatments but these are less frequent as compared to DHA-PPQ. From an individual patient meta-analysis of 5,487 subjects treated for *P. falciparum* with ASMQ, 49% of patients had at least one adverse event, 3.4% of subjects had early vomiting and the incidence of serious neurological reaction was 2 per 1,000.

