**Table 7a Proportions of patients that report a full course of observed TACT or ACT**

	AL, n/N (%), 95% CI)	A+AQ, n/N (%), 95% CI)	ASMQ, n/N (%), 95% CI)	ASMQ + PPQ, n/N (%), 95% CI)	p-value (AL vs AL+AQ)	p-value (ASMQ vs ASMQ+PPQ)
Completing full course of study drug	XXXX/XXXX (XX.X, XX.X - XX.X)	0.XXX	0.XXX			

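### No between-arm risk difference with a confidence interval is planned for TACT versus ACT safety, so the output will not show how large an excess risk remains compatible with the data

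*SAP*

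**What the plan says.** SAP section 3.4: "Safety and tolerability of TACTs versus ACTs will be assessed by comparing the frequency (%) of adverse events and serious adverse events". The sentence goes on to give particular attention to abdominal pain, appetite, "biochemical markers of hepatic and renal toxicity and QT interval prolongation, using the Fisher's exact test". Protocol 15.2.4 has the same text.

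The planned displays are:
- **Table 6:** n/N (%) per arm, with no difference, interval or p-value column.
- **Table 7a (completing the course):** on this endpoint section 3.4 says "The 95% confidence intervals will be reported for the proportions", meaning each arm's own proportion. There is one p-value column per matching pair; the first heading begins "p-value (AL vs AL+AQ".
- **SAP 3.5 and Table 8 (QTc change):** unpaired t-test at each time point; p-values only.
- **Protocol 15.2.1:** exact 95% intervals on crude proportions where relevant, not on differences.

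The efficacy shells (Tables 2a to 5a) do carry a risk difference with a 95% CI for each matching pair.

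On power, protocol 15.1 pools safety data across sites "to achieve the desired power of at least 80% to detect rare events", and works this out for an increase from 1 in 100 to 3 in 100. On rarer harms, protocol 3.1 gives a QTc rise above 60 ms on artemether-lumefantrine alone as "about 1 in 300 treatments". Protocol 19.4.3 says of ASMQ that "the incidence of serious neurological reaction was 2 per 1,000". Protocol 3.2 says of the earlier data that the "observations of low incidence of QTc prolongation are from a relatively small population, they need further monitoring and confirmation".

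**The concern.** Comparing the safety and tolerability of TACTs and ACTs is the first secondary objective. For a combination that adds a third drug, the useful question is how large an excess of harm the data can exclude. A test of equality does not answer it: two non-significant results can leave very different excesses open. Confirming that an incidence is low, which is what protocol 3.2 asks for, likewise needs an upper bound.

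At stake is what can be concluded about uncommon harms. Below the 1-to-3-per-100 design target, a non-significant Fisher result is likely even under a material relative increase. The planned tables give the reader no prespecified measure of what remains possible.

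**Working it through.** **Inputs**
- Arm sizes, Africa (protocol synopsis and 15.1): 72 ACT and 144 TACT per pair and site. The AL pair runs at 8 sites: 8 × 72 = 576 and 8 × 144 = 1,152. The ASMQ pair runs at 7 sites (not Rwanda): 504 and 1,008.
- Arm sizes, Africa plus Asia (protocol 15.1): AL 918 and 1,494; ASMQ 789 and 1,293.
- Base rates: 1/300 (protocol 3.1, AL) and 2/1,000 (protocol 19.4.3, ASMQ).
- Assumptions: two-sided 5% level, since the documents state none for safety; a tripling, carried over from the 1-to-3-per-100 target, since they state no target for rarer harms.

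**Method.** Power = Σ over all (x, y) of Bin(x; n_ACT, p_ACT) × Bin(y; n_TACT, p_TACT), counting only tables with two-sided Fisher p ≤ 0.05. Miss rate = 1 − power.

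**Step 1: the plan's own figure, 1% versus 3%**

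| Matching pair | Africa | Africa + Asia |
|---|---|---|
| AL | 77.8% | 92.5% |
| ASMQ | 70.6% | 88.0% |

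The stated power above 80% reproduces for Africa plus Asia. For Africa alone it reproduces with an unpooled z-test (86.6% and 81.9%), but not with Fisher's test at the assumed level.

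**Step 2: the documents' rarer harms, tripled**

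| Pair and event | Population | Expected events, ACT vs TACT | Power | Missed |
|---|---|---|---|---|
| AL, 1/300 to 3/300 | Africa | 1.9 vs 11.5 | 25.8% | 74% |
| AL, 1/300 to 3/300 | Africa + Asia | 3.1 vs 14.9 | 41.2% | 59% |
| ASMQ, 2/1,000 to 6/1,000 | Africa | 1.0 vs 6.0 | 6.1% | 94% |
| ASMQ, 2/1,000 to 6/1,000 | Africa + Asia | 1.6 vs 7.8 | 19.5% | 80% |

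The miss rate depends on the assumed ratio. For the ASMQ pair, a doubling from 2/1,000 is missed 94% (Africa + Asia) to 99% (Africa) of the time, and a fivefold rise 43% to 66%.

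**Step 3: what an interval would add.** Illustrative counts near the expected ones for the African ASMQ pair: 1/504 versus 6/1,008. Fisher p = 0.44.

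Newcombe interval: d = p_T − p_A; lower = d − √[(p_T − l_T)² + (u_A − p_A)²]; upper = d + √[(u_T − p_T)² + (p_A − l_A)²], where l and u are Wilson limits.

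- p_A = 0.198% (0.035 to 1.115); p_T = 0.595% (0.273 to 1.293); d = 0.397 points.
- Lower = 0.397 − √(0.322² + 0.917²) = −0.57.
- Upper = 0.397 + √(0.698² + 0.163²) = +1.11.

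An excess of up to 11 per 1,000 is not excluded. The African AL pair shows how different two non-significant results can be: 0/576 versus 0/1,152 has an upper limit of +0.33 points, while 1/576 versus 7/1,152 (p = 0.28) has +1.09.

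**Step 4: why crude pooling will not do.** Subtracting Africa from the pooled arms leaves 918 − 576 = 342 and 1,494 − 1,152 = 342 for AL, and 789 − 504 = 285 and 1,293 − 1,008 = 285 for ASMQ. The Asian part is therefore 1:1 against Africa's 1:2. It makes up 342/918 = 37% of the pooled AL arm but 342/1,494 = 23% of AL+AQ. If event rates differ between the studies, a crude difference mixes study with treatment.

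**The case against.** A reader might infer that safety is judged by Fisher p-values alone. It is not. Section 3.4 also plans descriptive summaries, an account of clinically relevant abnormalities, and per-arm intervals for course completion. SAP 3.5 uses a t-test for QTc change, and protocol 14.1 relates drug exposure to safety outcomes. None of these puts an interval on the between-arm difference.

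A reader might also infer that a non-significant result will be read as showing the TACT to be as safe. No passage sets such a rule. Protocol 3.2 describes the earlier trial's preliminary AL+AQ results as equally safe, but that is not a decision rule here. What stands is that the SAP gives no rule in either direction.

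The miss rates should not be quoted as one unconditional range of 59–94%: that would join two populations and hide the assumed tripling and level. At the design target, power in the Africa-plus-Asia pool is 88–92%. The 1/300 rate is sourced only for artemether-lumefantrine, so it is applied only to that pair. A QTc rise above 60 ms and serious neurological reaction are not rows of Table 6; they only show the scale of rare harms. For SAEs and QTc above 500 ms the documents give no base rate, so no miss rate can be stated.

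It is also fair to say that intervals do not raise power, that these are secondary endpoints, and that a reader could compute a crude interval from the planned counts. The last point holds only in part: a stratified difference cannot be recovered from pooled counts, and an interval chosen afterwards is not prespecified.

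**Conclusion.** The point holds as a gap in reporting and inference. Neither document plans a between-arm safety estimate with a confidence interval, so the output will not show how large an excess risk remains compatible with the data. The gap itself is read directly from the text and needs no assumption.

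Its size is an illustration, conditional on a tripling, a two-sided 5% level and full planned enrolment. Fisher's test would miss a 1/300 event in the AL pair 74% of the time (Africa) or 59% (Africa plus Asia), and a 2/1,000 event in the ASMQ pair 94% or 80%. With counts near those expected in the African ASMQ pair, p = 0.44 would coexist with a possible excess of about 1 per 100.

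The primary efficacy conclusion is not affected. The change is worth making because it alters what can be said about harm at almost no cost.

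**What to change.** In SAP section 3.4:

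1. **Estimate.** Report the risk difference, TACT minus ACT, with a two-sided 95% score or Newcombe interval for Table 7a and for the per-subject proportion rows of Table 6: SAEs, drug-related SAEs, QTc above 500 ms, graded symptoms and laboratory abnormalities.
2. **Comparisons.** Cover both matching pairs and the two non-matching comparisons that section 3.4 names.
3. **Stratification.** Stratify by site, and by study when Africa and Asia are pooled, because the allocation ratios differ. This also deals with Rwanda, which contributes to the AL arms only and so has no randomised non-matching comparison.
4. **Interpretation.** Keep Fisher's p-value as supportive. State that any conclusion of comparable safety will quote the upper confidence limit of the excess and will not rest on p > 0.05.
5. **Rows to treat differently.** Haemoglobin change needs a mean difference with an interval. Vomiting per number of treatments needs a method that allows for repeated doses within a subject.

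The cost is SAP wording, extra columns in Tables 6 and 7a and a little more programming, with no new data or patients. The downside is that safety statements become less categorical.
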